## **SUMMARY**

### **Rationale:**

**Objective:** To describe and evaluate the practice and safety of endotracheal intubation of patients in Dutch emergency departments (ED).

**Study design:** Retrospective cohort study.

**Study population:** Patients who underwent endotracheal intubation in the ED of one of the participating hospitals in the Netherlands

**Intervention (if applicable):** Not applicable.

**Main study parameters:** The practice of, indications for and incidence of complications of endotracheal intubation in the ED.

**Nature and extent of the burden and risks associated with participation, benefit and group relatedness:** Due to the retrospective design, there is no active involvement of patients or randomisation, and only data relevant to the study will be collected. Data collection will be completely anonymized.

## **1. INTRODUCTION AND RATIONALE**

Endotracheal intubation can be a lifesaving intervention for critically ill patients in the emergency department (ED). Endotracheal intubation is, however, a high-risk procedure with many potential complications, which seem to be even more prevalent when carried out in the ED compared to for example the operating theater(5). This is possibly due to multiple reasons such as a sicker population, non-elective setting, a higher variability among indications for intubation or competence of providers.

Internationally, large registries were established and multiple observational studies have been performed to gain more information about the methods, safety and complications of intubations in the ED. For example, a multicenter study in Australia and New Zealand set up the ANZEDAR (The Australian and New Zealand Emergency Department Airway Registry) and reported on the practice, indications, success rate and safety of 3710 intubations performed in emergency departments (1). The same was done with the NEAR (National Emergency Airway Registry) including ED's from the United States, Canada and Australia; in a prospective, multicenter international registry of intubations in emergency departments a total number of 17,583

intubations were registered and analyzed (3). These studies gave more insight into patient demographics, staff characteristics, pharmacologic agents used and complication rates. In the UK, a national audit project (NAP4) showed that there were relatively far more complications of airway management in the ED compared to the operating theater and that complications in the ED were more likely to result in harm or death than complications in the operating theater. Individual case review identified avoidable deaths and areas of care that need improvement (5,6).

While in recent years these studies have added to our knowledge of ED airway management, there is still a lack of high-quality studies and there is a strong argument for increased research. To date, no studies have been published of airway management in Dutch EDs. We therefore have no knowledge about any factors possibly influencing intubation outcomes and complications nor comparability with international data. Among these are factors that have been associated with preventable harm and death and insight into these factors could be used for improvement of the safety of airway management in Dutch EDs (6).

This study is therefore intended to provide a comprehensive review of the clinical practice and characteristics of endotracheal intubations within Dutch EDs. The results could potentially be used for comparative analysis against global datasets. Additionally, the insights gained from this study will shed light on existing gaps prevalent in the current registration processes of intubations in the Netherlands. Furthermore, these insights could act as a stepping stone for future investigations that can lead to a deeper understanding of the methodologies, safety protocols, and associated complications of endotracheal intubations within Dutch EDs.

## 2. OBJECTIVES

### **Primary outcome:**

Describing characteristics of the practice of endotracheal intubation in Dutch EDs, including information about patient demographics, indications for endotracheal intubation, intubation performer characteristics, equipment and medication used and complications due to intubation.

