### **5. METHODS**

#### **5.1 Study parameters**

- Intubator characteristics:
  - Specialty
    - Emergency medicine
    - Anesthesia
    - Intensive care medicine
    - Other
  - Seniority
    - Consultant
    - Resident

- Junior doctor

- Indication for intubation:
  - Trauma
  - Burns
  - Drowning
  - Overdose/ingestion
  - Respiratory failure
  - Cardiac arrest (active cardiac arrest)
  - Post-cardiac arrest
  - Stroke
  - Seizure
  - Altered mental status due to other cause (if altered mental status due to stroke, intoxication, seizure or post-cardiac arrest then score as the primary cause)
  - Sepsis
  - Cardiac failure
  - Airway obstruction
  - GI bleed
  - Anaphylaxis
  - Other
- Sedation agent used (Ketamine, etomidate, propofol, midazolam)
- Paralytic agent used (Rocuronium / Succinylcholine)
- Method of intubation
  - Direct laryngoscopy
  - Video (hyperangulated or direct)
  - Fiberoptic
  - Surgical airway
  - Use of airway adjuncts? If yes, which ...
- Patient characteristics: age (years), gender (male/female), weight/obesity (BMI).

- Vital parameters before intubation (respiratory rate, saturation, systolic blood pressure (SBP), heart rate).
- Was a pre-intubation airway assessment performed? Yes / no / missing
- If yes, were there any signs of a difficult intubation?
- Performance and mode of pre-oxygenation; no pre-oxygenation / nasal canula / NRM / mask ventilation / NIV / missing
- Was capnography used during intubation? Yes / no / missing
- The occurrence of complications of endotracheal intubation. Complications will be identified in two ways. The first option is that a complication is explicitly stated in the electronic medical record. The second option is that there are significant changes in vital signs as described in more detail below. The following complications will be registered:
  - significant decrease of peripheral oxygen saturation (SpO2). Defined as a desaturation of >10% from baseline or as defined by the treating physician
  - significant decrease of blood pressure. Defined as a systolic pressure <90mmHg with a drop of >20% from baseline or as defined by the treating physician.
  - significant increase of blood pressure. Defined as a systolic pressure > 160mmHg with a rise of >20% from baseline, or as defined by the treating physician.
  - significant bradycardia. Defined as a heart rate < 40/min and a drop of > 20% from baseline, or as defined by the treating physician.

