  - significant tachycardia. Defined as a heart rate > 160/min and a rise of > 20% from baseline, or as defined by the treating physician.
  - dental or airway trauma due to intubation attempt
  - oesophageal or mainstem bronchial intubation
  - vomiting or aspiration
  - laryngospasm
  - equipment failure
  - medication error
  - cardiac arrest
  - failed attempt / need for an emergency surgical airway
  - other, ....

For inclusion, complications should have occurred within 10 min of intubation, even if recognised after this time.

- As it is expected that complications of intubations are recorded in the electronic chart, the absence of notions of complications could be interpreted as an uncomplicated intubation. However, other physicians always explicitly mention that no complication occurred. Therefore, in this study the occurrence of complications can be coded as:
  - Complications occurred (complication specified)
  - No statement about complications
  - Explicitly stated that no complications occurred

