### **7. ETHICAL CONSIDERATIONS**

#### **7.1 Regulation statement**

The patients will not be asked for signed informed consent. The data collection will be retrospective and completely anonymized. Patients are not randomized. In addition, this research focuses on standardized care and no new or additional actions were carried out. We suspect to screen at least 500-1000 patients for inclusion and find it not feasible to ask every patient for consent retrospectively. This would cost a disproportionate amount of effort and possibly excludes a large number of patients due to not being able to reach the patient, especially since it is expected that a high proportion of the patients died due to the seriousness of the underlying disease. Also, to a lesser amount it may cause a selection bias because it could be more difficult to get consent in the case of complicated intubations. Data will be derived from electronic patient files, from 2019up to

now. Asking for informed consent from patients who had an intubation 3 years ago would not outweigh disadvantages for the patient.

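### The objective is worded causally, but the vital-sign route in section 5.1 has no attribution step, and about 7 of the 14 listed events can arise from the underlying disease

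*Combined protocol and SAP*

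**What the plan says.** The objective in section 2 covers "equipment and medication used and complications due to intubation". The Summary uses a looser phrase for the main parameters: "The practice of, indications for and incidence of complications of endotracheal intubation in the ED".

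Section 5.1 gives two ways of finding a complication:

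- From the record: "The first option is that a complication is explicitly stated in the electronic medical record".
- From the observations: "The second option is that there are significant changes in vital signs as described in more detail below".

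Five vital-sign items then have numeric limits, each with the treating physician's own judgement as an alternative. For low blood pressure the limit reads: "Defined as a systolic pressure <90mmHg with a drop of >20% from baseline". Of the remaining entries, one carries causal words, "dental or airway trauma due to intubation attempt". Another is simply "cardiac arrest", with no definition and no requirement that it be new. The one general restriction is that the complication occurred no more than 10 minutes from intubation.

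The indications in the same section include active cardiac arrest, the post-arrest state, sepsis, gastrointestinal bleeding, trauma and cardiac failure. Section 4.3 excludes only patients whose chart has no information on the intubation. Section 6 presents nominal data as numbers and percentages. It mentions comparison across treatment groups without defining them, and it specifies no breakdown of complications by indication or by the patient's state before intubation.

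**The concern.** The objective makes a causal statement, while the numeric route depends only on size and timing of a change. In a patient with sepsis, bleeding or a recent arrest, a further fall in pressure, a rise in heart rate or another arrest within minutes may be the course of the illness. If such a change meets a limit, the plan reports it as a complication of the procedure.

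This affects how the results can be read. Section 1 suggests that findings could be used to improve airway safety and could be compared with datasets from other countries. It also names a sicker population and more varied indications as possible reasons for higher complication rates in the ED. A rate of physiological events that is not broken down by indication can differ between hospitals or countries because of case mix alone, with identical airway care.

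**Working it through.** The plan states no expected complication rate, event count or share of patients by indication, so there is no figure of its own to reproduce. The check has four parts.

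**1. Which entries are affected.** Section 5.1 lists 14 entries.

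| Group | Entries | Count |
|---|---|---|
| Can arise from the disease | desaturation, hypotension, hypertension, bradycardia, tachycardia, vomiting/aspiration, cardiac arrest | 7 |
| Procedural, or largely so | airway trauma, oesophageal/mainstem placement, laryngospasm, equipment failure, medication error, failed attempt/surgical airway | 6 |
| Open | other | 1 |

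7 + 6 + 1 = 14. The grouping is a judgement on the nature of each event, so 7 is approximate.

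**2. What the baseline condition removes.** The hypotension item needs a systolic pressure below 90 mmHg and a drop of more than 20%. The two conditions meet at 90 / 0.80 = 112.5 mmHg.

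- Baseline 112.5 mmHg or higher: any value below 90 qualifies.
- Baseline 100 mmHg: the value must be below 100 × 0.80 = 80.
- Baseline 80 mmHg: the value must be below 80 × 0.80 = 64.

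A patient in shock whose pressure does not change is not counted by the numeric rule. A patient whose disease takes the pressure from 115 to 85 mmHg within 10 minutes is counted. The other pressure and heart-rate items also require a change of more than 20%, and desaturation a fall of more than 10%, so the same reasoning applies to them.

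**3. How arrest is counted.** Cardiac arrest has no numeric limit, so it presumably enters through the record. The text does not settle whether a charted re-arrest that nobody called a complication would count. Nor does it say what is done with a patient already in arrest when intubated, for whom a percentage change from baseline pressure or heart rate has no clear meaning.

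**4. How case mix could act, with assumed values only.** Let p be the share of post-arrest patients, a their rate of disease-driven re-arrest in the window, and 1% the rate in all others, and suppose that re-arrests are counted. The overall rate is p × a + (1 − p) × 1%.

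| a | p = 5% | p = 10% | p = 20% | Part from post-arrest patients at p = 10% |
|---|---|---|---|---|
| 15% | 0.75 + 0.95 = 1.7% | 1.5 + 0.9 = 2.4% | 3.0 + 0.8 = 3.8% | 1.5 / 2.4 = 63% |
| 3% | 0.15 + 0.95 = 1.1% | 0.3 + 0.9 = 1.2% | 0.6 + 0.8 = 1.4% | 0.3 / 1.2 = 25% |

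Whenever a exceeds 1%, the overall rate rises with p while airway care stays the same. How much it rises depends almost entirely on a, which the documents do not give.

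**The case against.** The strongest reply is that this is a descriptive study, for which a time-based definition is normal. The list stands under a heading on complications of intubation, the record route involves clinical judgement, and the 10-minute sentence restricts complications rather than turning every event into one. Definitions may also be given in the abstraction form and the abstractor manual, which are not in the supplied text. Much of this stands. A time-based definition is reasonable; the weakness is that its result carries a causal label. Wherever an attribution rule may sit, it defines the outcome and belongs in the main text.

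A reader might infer more than the documents support:

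- *That every entry except airway trauma is counted whatever its cause.* Only that entry has causal words, but oesophageal or mainstem placement, equipment failure, medication error and failed attempt are procedural by nature, and laryngospasm largely so. The absence of attribution is certain only for the numeric vital-sign route.
- *That established shock or re-arrest is necessarily reported as harm.* Unchanged shock is filtered out by the baseline condition, and the coding of re-arrest is unclear rather than settled.
- *That section 6 pools everything into one headline percentage.* It defines no composite, and section 5.1 has each complication specified. What is missing is a planned breakdown.
- *That section 7.1 concedes the point in saying that "it is expected that a high proportion of the patients died due to the seriousness of the underlying disease".* That sentence supports the waiver of consent and concerns death at any time, not deterioration within 10 minutes.

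A further objection is that relabelling could hide events that intubation did cause. It would not if all of them are still counted and tabulated; only the claim about cause is withdrawn.

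**Conclusion.** The concern holds in a limited form. The causal wording of section 2 is stronger than the numeric vital-sign route can support, and the supplied text leaves ongoing and recurrent arrest uncoded. About 7 of 14 entries are affected. An overall rate for those items will partly reflect the mix of indications.

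The size is unknown. The calculation above shows a direction and how sensitive it is to one assumption; neither 63% nor 25% is an estimate for this cohort. The conclusion rests on the grouping of the entries and on there being no attribution rule in the unseen form or manual. If one exists there, the remaining need is to state it in the protocol and to report by indication. This is a worthwhile, inexpensive improvement; it does not invalidate the study.

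**What to change.** **Wording (Summary, sections 2 and 5.1).** Describe the seven items as adverse events within 10 minutes of intubation, and state that no causal attribution is made for them. Keep the term complication due to intubation for the six procedural entries. Classify each entry under other according to the event specified.

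**Arrest (section 5.1).** State that the arrest event means a new arrest. Show patients intubated during active arrest separately, and leave them out of the denominator for the arrest and vital-sign items.

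**Reporting (section 6).** Alongside the overall figure, report the seven items by indication group (active arrest; post-arrest; sepsis, gastrointestinal bleed, trauma or cardiac failure; other) and by pre-intubation systolic pressure (below 90 mmHg against 90 mmHg or above). Add a row for missing pressure, in line with section 5.2.4.

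**Cost.** Wording and one table from variables already collected. The downside is small strata and a less simple overall figure. For scale, section 7.1 expects to screen at least 500 to 1,000 patients; if that many were included and a group made up an assumed 10%, it would hold 50 to 100 patients.

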### **3. STUDY DESIGN**

This is a retrospective cohort study using electronic patient charts of patients who underwent endotracheal intubation in the emergency departments of the participating hospitals.

### **4. STUDY POPULATION**

#### **4.1 Population (base)**

Patients undergoing endotracheal intubation in the emergency department of one of the participating hospitals.

#### **4.2 Inclusion criteria**

Patients who underwent endotracheal intubation between 01-01-2019 and 31-12-2023 in the participating ED's.

#### **4.3 Exclusion criteria**

Patients for which no information about the intubation can be found in the electronic patient chart will be excluded from the study.

#### **4.4 Sample size calculation**

Not applicable. Data of all patients eligible for the study will be included.

### **5. METHODS**

#### **5.1 Study parameters**

- Intubator characteristics:
  - Specialty
    - Emergency medicine
    - Anesthesia
    - Intensive care medicine
    - Other
  - Seniority
    - Consultant
    - Resident

- Junior doctor

- Indication for intubation:
  - Trauma
  - Burns
  - Drowning
  - Overdose/ingestion
  - Respiratory failure
  - Cardiac arrest (active cardiac arrest)
  - Post-cardiac arrest
  - Stroke
  - Seizure
  - Altered mental status due to other cause (if altered mental status due to stroke, intoxication, seizure or post-cardiac arrest then score as the primary cause)
  - Sepsis
  - Cardiac failure
  - Airway obstruction
  - GI bleed
  - Anaphylaxis
  - Other
- Sedation agent used (Ketamine, etomidate, propofol, midazolam)
- Paralytic agent used (Rocuronium / Succinylcholine)
- Method of intubation
  - Direct laryngoscopy
  - Video (hyperangulated or direct)
  - Fiberoptic
  - Surgical airway
  - Use of airway adjuncts? If yes, which ...
- Patient characteristics: age (years), gender (male/female), weight/obesity (BMI).

- Vital parameters before intubation (respiratory rate, saturation, systolic blood pressure (SBP), heart rate).
- Was a pre-intubation airway assessment performed? Yes / no / missing
- If yes, were there any signs of a difficult intubation?
- Performance and mode of pre-oxygenation; no pre-oxygenation / nasal canula / NRM / mask ventilation / NIV / missing
- Was capnography used during intubation? Yes / no / missing
- The occurrence of complications of endotracheal intubation. Complications will be identified in two ways. The first option is that a complication is explicitly stated in the electronic medical record. The second option is that there are significant changes in vital signs as described in more detail below. The following complications will be registered:
  - significant decrease of peripheral oxygen saturation (SpO2). Defined as a desaturation of >10% from baseline or as defined by the treating physician
  - significant decrease of blood pressure. Defined as a systolic pressure <90mmHg with a drop of >20% from baseline or as defined by the treating physician.
  - significant increase of blood pressure. Defined as a systolic pressure > 160mmHg with a rise of >20% from baseline, or as defined by the treating physician.
  - significant bradycardia. Defined as a heart rate < 40/min and a drop of > 20% from baseline, or as defined by the treating physician.
  - significant tachycardia. Defined as a heart rate > 160/min and a rise of > 20% from baseline, or as defined by the treating physician.
  - dental or airway trauma due to intubation attempt
  - oesophageal or mainstem bronchial intubation
  - vomiting or aspiration
  - laryngospasm
  - equipment failure
  - medication error
  - cardiac arrest
  - failed attempt / need for an emergency surgical airway
  - other, ....

For inclusion, complications should have occurred within 10 min of intubation, even if recognised after this time.

- As it is expected that complications of intubations are recorded in the electronic chart, the absence of notions of complications could be interpreted as an uncomplicated intubation. However, other physicians always explicitly mention that no complication occurred. Therefore, in this study the occurrence of complications can be coded as:
  - Complications occurred (complication specified)
  - No statement about complications
  - Explicitly stated that no complications occurred

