### 5.2.1 Identification of subjects

We will collect data by searching the database via one or multiple ways, depending on the local registration infrastructure of the hospital. Options are searching for procedural code for endotracheal intubation, screening ICU admissions, screening resuscitation room logbooks, screening medication logbooks for intubation medication, searching ICD-10 code for cardiac arrest and other pathologies that could lead to intubation.

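### No field records ED disposition or whether a post-ED record exists, so complications that can be recognised late may be under-detected in patients with short records

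*Combined protocol and SAP*

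**What the plan says.** Section 5.1 gives two routes to a complication. On the first: "The first option is that a complication is explicitly stated in the electronic medical record". On the second: "The second option is that there are significant changes in vital signs as described in more detail below". The timing rule is that "complications should have occurred within 10 min of intubation, even if recognised after this time". Occurrence is thus bounded at 10 minutes and recognition is not bounded at all.

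The data source is set in section 3: "This is a retrospective cohort study using electronic patient charts of patients who underwent endotracheal intubation in the emergency departments of the participating hospitals". Neither section says which parts of the chart are read for complications (ED notes, imaging reports, ICU or ward notes, discharge letter) or how far forward.

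The complication list in section 5.1 includes "oesophageal or mainstem bronchial intubation", aspiration, and dental or airway trauma. Each chart then receives one of three codes: a complication occurred, "No statement about complications", or an explicit entry that there was none. Disposition, death in the ED, transfer and length of available record are not among the listed parameters.

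Section 7.1, explaining why consent is not sought, remarks that "it is expected that a high proportion of the patients died due to the seriousness of the underlying disease". Section 5.2.1 lets each site find its patients by one or more routes, "depending on the local registration infrastructure of the hospital".

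**The concern.** With recognition left open, the time available to detect a complication is as long as the patient's record. A patient admitted to the ICU may have days of notes and imaging in which a mainstem placement or an aspiration can surface. A patient whose record stops early has little or nothing beyond the ED note. For items that can be recognised late, a recorded event depends on both its occurrence and the chance to see it, and the planned dataset does not separate the two.

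Complications are part of the primary outcome in section 2, and section 1 foresees comparison with datasets from other countries. That comparison needs a stated detection window. Section 5.2.2 adds a reason to act early: the abstracted data cannot be linked back to individual patients. If disposition and record availability are not captured at abstraction, they may not be recoverable, and unequal detection could then not be examined.

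**Working it through.** The plan states no complication rate, sample size or power, so there is no figure to reproduce. The check has a textual part and an illustration.

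**Text.** Four statements, read together, leave the gap:

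- Section 5.1 bounds occurrence but not recognition.
- Sections 3 and 5.1 name the chart but not its depth.
- Section 5.1 lists no disposition or record-length variable.
- Section 7.1 expects many deaths, and section 5.1 lists active cardiac arrest as an indication, so some short records are foreseeable.

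**Illustration, any complication.** All four inputs are assumptions, because the documents supply none of them:

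- *p*, true risk of any complication, taken as equal in all patients: 20–30%
- *L*, share of affected patients whose only complication is recognised late: 5–30%
- *s*, share of patients with a short record: 10–50%
- *d*, chance that such a complication is still recorded in a short record: 0 or 0.5

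Observed risk in short-record patients = p × (1 − L + L × d).

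Observed overall risk = (1 − s) × p + s × (observed risk in short-record patients), so the overall shift is s × p × L × (1 − d).

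| Case | p | L | s | d | Short-record group | Overall |
|---|---|---|---|---|---|---|
| Smallest | 20% | 5% | 10% | 0.5 | 19.5% (−0.5 points) | 19.95% (−0.05) |
| Middle | 30% | 10% | 30% | 0 | 27.0% (−3.0) | 29.1% (−0.9) |
| Largest | 30% | 30% | 50% | 0 | 21.0% (−9.0) | 25.5% (−4.5) |

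Middle case written out: 0.30 × (1 − 0.10) = 0.270; 0.70 × 0.30 + 0.30 × 0.270 = 0.291.

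If L is 5%, the overall shift is at most 0.50 × 0.30 × 0.05 = 0.75 points. If L is zero there is none.

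**Scale.** Section 7.1 expects to screen at least 500–1000 patients. Taking these as the included numbers, the 95% half-width is 1.96 × √(p(1 − p)/N):

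- N = 500: 3.5 points at p = 20%, 4.0 at p = 30%
- N = 1000: 2.5 points at p = 20%, 2.8 at p = 30%

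**Illustration, one late-recognisable item.** Assume a true risk of 5%, a short-record share of 20–40%, and a fraction *e* of events already seen in the ED. Observed rate = 5% × [1 − s × (1 − e)].

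- e = 0: 5% × 0.80 = 4.0% down to 5% × 0.60 = 3.0%
- e = 0.5: 5% × 0.90 = 4.5% down to 5% × 0.80 = 4.0%

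The relative under-count is s × (1 − e). It is the assumption restated, and the documents do not supply it.

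**The case against.** The strongest reply is that the plan already treats silence as ambiguous. A chart that says nothing is coded "No statement about complications", apart from an explicit denial, so a reader who infers that patients without later records enter the percentages as event-free goes beyond the text. That stands. The code does not close the gap, however. It appears to apply per patient, so a patient with recorded hypotension counts as complicated even if mainstem placement was never looked for. An ED note denying complications gets the explicit code although no later record could contradict it. Nor does the plan say how the silent category enters a denominator.

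Second, the abstraction form is an appendix and section 5.2.3 promises a manual, training and meetings on coding rules. None of that content is in the supplied text, and it may fix what is to be read. This also stands. If it does, the rule need only be stated in the protocol. Pilot testing, and kappa on 10% of charts covering the incidence of complications, address disagreement between abstractors. They cannot reveal an event missing from a short chart, because both abstractors would miss it.

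Third, most listed complications do not depend on late recognition. Vital-sign events have their own route, and cardiac arrest, failed attempt and laryngospasm are normally evident at once. That split is a clinical judgement without figures in the documents, but it is reasonable and limits the effect on the overall rate.

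Fourth, section 7.1 says neither when nor where patients died. Some will have died after ICU admission, with later notes on file. The documents do not mention transfer between hospitals.

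**Conclusion.** The point holds as a cheap improvement. The recognition period has no stated end, the depth of chart search is not given in the supplied text, and no listed field would let anyone check whether detection differed with the length of the record. Mainstem placement, aspiration, and dental or airway trauma may be under-detected in patients with short records.

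Size and direction cannot be derived from the documents. The illustration yields only downward shifts because it assumes equal true risk and no later misattribution, so it cannot establish direction. In the middle case the overall rate moves by 0.9 points, well inside the sampling error. A shift as large as the sampling error needs the extreme assumptions together. The rates of the individual late-recognisable items are more exposed.

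A reader might infer that risk in patients who die in the ED or are transferred is understated as a matter of fact, or that hospitals with more transfers will look safer. The documents support neither. They do not place the deaths in the ED, do not mention transfer, and plan no comparison by hospital or disposition; section 6 refers only to treatment groups. A relative under-count of 20–40% would likewise be no finding, since it repeats an assumed share of short records.

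**What to change.** Before abstraction starts:

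- Add a field for ED disposition (died in ED, admitted, transferred out) and one for later record available (yes/no).
- Flag each complication as recognised in the ED or later.
- Report mainstem placement, aspiration, and dental or airway trauma (a) as recognised in the ED, for all patients, and (b) as recognised at any time, both for all patients and for those with a later record. State how the code "No statement about complications" enters each denominator.
- State in the protocol which record sections and what time span are searched for complications, the same at all sites. If the manual or form already says so, copy the rule across.

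A 24-hour cap on recognition is not required. It would drop events found later, for example at extubation, and would not equalise detection for patients who have no record after the ED.

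The cost is a few form fields, one extra denominator and a short addition to the manual. The subset with a later record is selected on survival, so its rate should stand beside the all-patient rate and not replace it.
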